### **Research Design and Methods**

#### *Design*

This 3-year, mixed methods modified, non-randomized trial will follow individuals for two years. Due to the inability to recruit veterans interested in participating in a control (no dog) group, this group has been eliminated going forward with the study. The study will examine the influence of SDs by assessing the longitudinal change in mental health assessment over time among veterans who have PTSD. The group will consist of individuals partnered with SDs. Following initial screening for inclusion criteria, including criteria set by dog vendors, subjects who are eligible will receive a SD. This study will measure changes over time in the primary outcome of mental health. Additional outcomes in psychosocial health and healthcare utilization will be included. Recruits successfully completing the screening process will be placed on a vendor's waiting list to receive a SD upon the dog's completion of training. Recruits who do not meet all criteria, including vendor criteria, will be ineligible to participate..

Data will be collected at baseline and at 3, 6, 9, 12, 18 and 24 months for individuals with service dogs. For those awaiting service dogs, repeated assessments will occur every 3 months until obtaining a SD. Once baseline data has been collected for 24 months, assessments will occur every 6 months until the Veteran is paired with a SD. Baseline data will include detailed information on the characteristics of the participants, their mental health, psychosocial well-being, socioeconomic and healthcare utilization characteristics. As we want to obtain information regarding the changes in health and wellbeing over time, a prospective study will permit this type of comparison.

*Sample:* The study will use a convenience sample of VHA patients who are currently in treatment for PTSD. We have chosen to use these criteria as a safety measure for the veteran and the dogs. At this time, there are currently 600 veterans receiving care at James A. Haley VAMC for PTSD, with an estimated 25 new veterans seen in the clinic per week. We are confident that an adequate number of Veterans will be recruited for the study. We will monitor recruitment and retention numbers on a monthly basis. The use of additional VA hospitals as a potential source for recruitment is the contingency plan should we be unable to meet enrollment numbers.

We will be enrolling up to 220 Veterans to be paired with service dogs. The previously cited longitudinal study had only an eight percent attrition rate. Although similar methods are included in this proposal, we recognize that this is a different population; we will plan on a higher attrition rate. Thus, we are estimating a 15 percent drop-out rate ( $n=33$ ), and we will over-recruit participants. Up to two hundred and twenty participants will be recruited over the course of the study. These recruitment numbers are chosen with the expectation that *200 individuals* will complete the study.

A repeated measures design with one fixed effects (any one covariate [TBD]) and 1 within subject effect (time; each subject is measured 5 times [minimum]) achieves approximately 100% power to test the primary fixed effect (dog group status) if a Geisser-Greenhouse Corrected F Test is used with an alpha level=5% and the actual effect  $SD=0.47$  (effect size=5.54). Further, this design achieves approximately 100% power to detect a significant effects among both covariates (alpha level=5%,  $SD=0.8$ ; effect size=5.54) and significant interaction between both the primary fixed effect (dog group status) and each of the covariates (alpha level=5%,  $SD=0.8$ ; effect size=5.54). This analysis assumes a 1st order auto correlation between repeated assessments equal to 0.80.

To assure that we recruit sufficient sample size, we will initiate the following strategies: (1) carefully consider respondent burden when finalizing the baseline survey and interview schedule, (2) employ and train research assistants/data collectors with previous experience in collecting data and who have good communication skills, (3) provide a small reimbursement (\$10.00) for participant time and effort each time a questionnaire is returned, (4) develop posters and recruitment flyers which will be displayed in all mental health clinical areas, and (5) provide in-services on a regular basis to the PTSD and other mental health clinicians explaining the study. These methods have been used successfully in the past by the research team.

The investigators will track all subjects who contact them for potential participation in the study. Reasons for individuals deciding not to participate will be tracked. In the past, reasons that have been recorded include time, and effort to make appointments. The eligibility criteria will also be tracked so that a description of the population and who met criteria to enter the study (or not) can be described for future publications. These methods are used in all studies that the PI conducts.

To assure that we retain sufficient sample size, we will initiate the following strategies: (1) coach the research assistants in establishing rapport during all contact (in person and telephone), (2) reminders sent in advance of in-person interviews and packet of information sent to participant two weeks prior to the time of their scheduled interview, alerting the participant that we will be calling, (3) at the end of all visits, provide the participants the phone number with which to contact researchers should they have to change their next visit, as well as provide the name and

phone number of the supervisor should they have problems (4) send out a thank you card once a year to let participants know their efforts are appreciated, (5) keep the interviews to a minimum to lessen respondent burden, and (6) conduct quality assurance for the visits to assure that participants are being interviewed appropriately. These methods have been used successfully in previous studies conducted by the PI.

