#### *Inclusion/Exclusion Criteria*

Inclusion Criteria	Description
Age	Age greater than or equal to 18 years
Referral	Referral from VA provider which documents PTSD diagnosis.
PTSD	PTSD symptoms as documented in the clinician referral letter.
Treatment for PTSD	In active treatment for PTSD for at least three months at time of enrollment and remain in treatment throughout the duration of the study. Participation will be verified quarterly to ensure that the veteran is still in treatment.
Acceptance by the dog vendor	Will be a function of the vendors that agree to provide dogs.
Dog care	Ability to adequately care for a dog, physically/financially. Has suitable home environment to provide for a dog. Has someone to care for a dog in the absence of the Veteran.
Travel to vendor	Willing and able to travel to vendor location by air or car for pairing
Geographic location	Living the state of Florida

Exclusion Criteria	Description
Mental Health Hospitalization	Veterans will be excluded if they have been hospitalized for mental health reasons in the prior 6 months.
Residence	Not living at the same residence for 6 months. It will be emphasized to the subjects to try and maintain the same residency throughout the duration of the study. Rationale is to ensure access they have appropriate follow up available to them both clinically and for the service dog.
Specific Diagnoses/conditions	Psychoses, Delusions, dementia, active alcohol/substance abuse or dependence, moderate to severe TBI as documented by chart review, suicide flag in CPRS. Study staff identifies a social, mental, or physical condition that prevents the Veteran from giving informed consent or participating in the study

Active suicide /homicide	At time of entry – Active suicide/homicide plan or intent, cognitive disabilities that would preclude safety of animal and ability needed for participation in the study
Children under 10	Veterans with children under 10 years of age in the home for more than 8 hours per day one day a week or more will be unable to participate.
Dual Enrollment without approval	While in this research study participants are required to check with the study team prior to enrolling in a secondary study. Taking part in other research studies may invalidate the results of this research, as well as that of the other research. As a result, participation in this study may be terminated.

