*Intervention:* The vendor(s) will provide SDs for the Veterans enrolled in the study. The dogs will be trained according to their standards and will meet the criteria outlined in the Statement of Work (SOW). All dogs will be trained in basic obedience and a standard set of commands related to mitigation of PTSD symptoms. Due to previous vendor issues, the updated SOW calls for vendors to use only purpose bred dogs (no rescues) which have passed a thorough medical work up and have been “proofed” by a VA dog trainer with extensive experience in training dogs. Veterans will be expected to follow all directions from the vendor(s). Should a Veteran need hospitalization for mental health reasons at any time after they are enrolled, they will not be dropped from the study. Veterans must remain in active treatment for PTSD for the duration of the study. Any Veteran who stops receiving treatment for their PTSD symptoms will be dropped from the study and the service dog removed and returned to the vendor. To ensure Veterans are still in treatment, quarterly verification of mental health treatment will be done by contacting the Veteran’s clinician directly or reviewing the medical record..

Once a Veteran has completed their participation in the study, they may choose to keep their dog or return it to the vendor. If the Veteran chooses to keep their dog at the end of their study participation, they take full responsibility for the care of the dog. Neither the study nor the VA provides further support to the Veteran to care for the dog upon completion of the two year period. If keeping their dog, Veterans may be required to return the dog’s service vest to the vendor who provided it. Once out of the study, the Veteran will be able to contact the vendor directly and receive any follow up services provided by the vendor. Such services may include training support, supplies, support groups, or other services.

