### Other Forms

Form	Purpose	When Completed	Who Completes
Home environment checklist	Checklist to assess home environment prior to dog placement	Pre-pairing home visit	Study Team Dog Trainer
Dog Care Test	Test knowledge of dog care and responsibility	After completion of Dog Care Course	Veteran
Service Dog Post Pairing Evaluation	Assess pairing and identify potential health or behavior problems in dogs	One week post pairing, months 1, 2, 3, 6, 9, 12, 18, 24	Study Team Dog Trainer at home visit
Veterinarian Checklist	Assess dog's health	Once per year	Veterinarian caring for each dog
Veteran Guide for Veterinary Care	Provides information to Veteran about maintain dog's health	Provided when Dog Care Course is completed	Information provided to Veterans
Home visit information sheet	Provides information to Veterans about how and why the home visit is done	Provided after IC, prior to home visit	Information provided to Veterans

Service Dog Questions	Veteran's subjective report about the dog's behavior and Veteran's satisfaction with the dog	Months 3, 6, 9, 12, 18, 24	Study team member present at home visit
-----------------------	--	----------------------------	---

Unless otherwise noted, all measures are completed at all visits.

\*\*Data for these items will be abstracted from medical record

Mental Outcomes: Outcomes for the main hypotheses will be measured with the following measure using the PTSD Checklist (PCL). PTSD Checklist is a 17-item self-report measure of the 17 DSM-IV symptoms of PTSD. Respondents rate how much they were “bothered by that problem in the past month”. Items are rated on a 5-point scale ranging from 1 (“not at all”) to 5 (“extremely”). The PCL can be scored in several different ways. A total score (range 17-85) can be obtained by summing the scores from each of the 17 items. Although the CAPS was used initially for the study, it was decided by the research team with input from the funding agency that diagnosis of PTSD will be confirmed by referring clinician and eliminate stress of completing the interview for the veteran. For some of the veterans that are enrolled in the study, CAPS is available in their medical record. If it is available, we will abstract the information to further confirm the diagnosis.

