*Alcohol Use Disorder Identification Test (AUDIT-C) and/or Addiction Severity Index –Alcohol Use Disorders Identification Test (AUDIT)-C is a 3-item paper and pencil alcohol screen to identify hazardous drinking or those with problematic alcohol consumption use (abuse and dependence). There is a five-point scale ranging from 0 to 4. The items are summed to obtain a total score ranging from 0-12. For men, a score of 4 or more is considered positive. For women, a score of 3 or more is considered positive. Internal consistency reliability has been reported as 0.80.*

Physical factors: Physical factors will include items that can be drawn from the medical record (co-morbidities, medications). Abstracting medical record data at least one year prior allows for an evaluation of trends or sudden departures from normal care or medication profiles. *In addition, we will track the number of visits and type of therapies that the subjects will be participating in while in treatment for their PTSD.*

*Pittsburgh Sleep Quality Index (PSQI) is a 24 item self-administered survey used to assess sleep-related problems during the past month. The first 19 items are completed by the subject and there are five items completed by a bed partner or roommate. The five items answered by a bed partner or roommate are used as clinical information and are not included in scoring. The first 19 items are grouped into seven components (sleep quality, sleep latency, sleep duration, habitual sleep efficiency, sleep disturbances, use of sleep medication, and daytime dysfunction) each weighted equally on a 0-3 scale. The seven component scores are then summed to yield a global score, which has a range of 0-21; higher scores indicate worse sleep quality. The seven component scores of the PSQI had an overall reliability coefficient (Cronbach's  $\alpha$ ) of 0.83. We will also be using the PSQI-A, addendum for PTSD. The PSQI-A asks an additional ten questions that target PTSD-related sleep problems.*

Psychosocial factors:

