**Analysis:** The distribution of each variable will be examined for outliers to determine if transformations (to normalize data) are necessary. Initially, means  $\pm$  SD, and medians, will be calculated for all continuous measures (e.g., age, psychological scales). Frequencies and percent will be determined for categorical variables (e.g., gender, race, etc.). Variables considered ‘confounders’ (demographic and dog predisposition questionnaires) would be compared across time for the relevant hypotheses. Categorical variables (e.g., gender, race, disability) will be compared across groups using chi-square. Continuous variables (years of disability, dog predisposition scores) will be compared using ANOVA. Baseline differences will be noted and controlled for in additional analyses. A significance level of ( $\alpha < 0.05$ ) will be used for all analyses. All data will be managed as intent to treat.

Statistical Analyses are presented below by hypothesis:

**Hypothesis 1A:** *Individuals partnered with SDs will have greater improved mental health over time.* Baseline data will be examined. Observed significant differences will be used as covariates in modeling, they will be controlled in subsequent analysis. For this hypothesis, a linear repeated measures mixed model will be used to determine changes over time between groups. PCL-checklist scores will be considered the dependent variable. Baseline PCL-C scores will be introduced in all models as covariates. These scores are continuous. The use of mixed models allows for control of covariance data expected in clustered and repeatedly sampled data, and missing data. We expect the SD group to have greater functional independence and community participation at the end of the study.

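### With no control group and PTSD treatment mandatory throughout, a fall in PCL under Hypothesis 1A cannot be assigned to the service dog, and the model ignores the pre-pairing data that would help

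*Combined protocol and SAP*

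**What the plan says.** The Design section reports that recruitment to the no-dog control failed and that "this group has been eliminated going forward with the study". It then sets out how the dog's influence will be judged: "The study will examine the influence of SDs by assessing the longitudinal change in mental health assessment over time among veterans who have PTSD".

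The Inclusion Criteria require each Veteran to be "In active treatment for PTSD for at least three months at time of enrollment and remain in treatment throughout the duration of the study". The Intervention paragraph repeats the condition, "Veterans must remain in active treatment for PTSD for the duration of the study", and says that Veterans who stop treatment are dropped and the dog is returned.

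The primary outcome is the PCL: "A total score (range 17-85) can be obtained by summing the scores from each of the 17 items". For Hypothesis 1A the Analysis section says that "a linear repeated measures mixed model will be used to determine changes over time between groups" and that "PCL-checklist scores will be considered the dependent variable", with baseline PCL as a covariate. It names no therapy or medication term and does not restrict how a fall in PCL may be described.

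Two sets of relevant data are collected but do not appear in that model. Under Physical factors, "we will track the number of visits and type of therapies that the subjects will be participating in while in treatment for their PTSD", and Table 2 lists medication type, class and dose. The Design and Recruitment sections also schedule assessments every 3 months while a Veteran waits for a dog, then every 6 months after month 24, with withdrawal if no pairing has occurred by month 48.

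**The concern.** Aim 1 is to determine the impact of service dogs, and Aim 3 turns the findings into recommendations on providing them. Both need change to be attributable to the dog. PTSD treatment targets the same score, and every participant receives it by rule for the whole period. With one group, pairing, treatment and the passage of time all act on the same people in the same months. Effective background care alone could lead to Hypothesis 1A being declared supported. The plan's own Background section criticises earlier research for lacking adequate control groups.

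The choice of baseline matters too. Assessments are repeated during a wait that may last years, and the text does not say which one is the baseline. If it is the score at consent, any drift during the wait is added to the apparent dog effect.

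**Working it through.** **The plan's own figures.** The Sample section states about 100% power for dog group status, with effect size 5.54, effect SD 0.47, alpha 5% and first-order autocorrelation 0.80. It gives neither units nor a group size, so the inputs do not fix one calculation. Two readings show this:
- As a ratio of effect SD to error SD, 5.54 gives power of 1.00 even with 5 per group, but implies an error SD of 0.47/5.54 = 0.085, which is not on the PCL scale.
- As 5.54 PCL points with SD 5.54/0.47 = 11.8 and 100 per group, power on one visit is 0.91.

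Either way, the effect powered is a group contrast that a one-group study no longer has. For sample size, 220 × 0.15 = 33 reproduces and leaves 220 − 33 = 187, although the text expects 200 completers.

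**Inputs for the check.**
- From the documents: N = 187; correlation 0.80 per visit; seven visits (0, 3, 6, 9, 12, 18, 24 months); alpha 5%, taken as two-sided.
- Assumed: PCL SD 12, range 10 to 15; test contrast = mean of the six post-dog visits minus baseline. The Analysis section does not write this contrast. It is one reasonable reading of what is left.

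**Standard error.** With correlation 0.8^|i−j|, in units of SD²:
- variance of the baseline score: 1
- variance of the mean of six follow-up scores: 0.680
- covariance of that mean with baseline: 0.492
- variance factor: 1 + 0.680 − 2 × 0.492 = 0.696

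SE = SD × √(0.696/187) = 0.61, 0.73 and 0.92 points for SD 10, 12 and 15.

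**Chance of rejection with no dog effect.** For a background mean fall d this is Φ(d/SE − 1.96).

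| Mean fall d | SD 10 | SD 12 | SD 15 |
|---|---|---|---|
| 1 point | 37% | 28% | 19% |
| 2 points | 91% | 78% | 59% |
| 3 points | 99.8% | 98% | 91% |

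**Mean fall is not final drift.** The six visits average (3 + 6 + 9 + 12 + 18 + 24)/6 = 12 months. A linear drift reaching 2 points at month 24 is therefore a mean fall of 2 × 12/24 = 1 point, and belongs in the first row.

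**Other readings (N = 200, SD 8 to 15).**
- Baseline-to-final change, correlation 0.80 between those two visits: 1 point rejects 32 to 79%, 2 points 84 to 100%.
- Same change, correlation decaying over five or seven visits: 1 point 12 to 37%, 2 points 34 to 90%.
- Geisser-Greenhouse F test for time, seven visits, linear drift: 1 point 10 to 26%, 2 points 29 to 81%.

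All exceed 5%. One reading behaves differently. If baseline is only a covariate and time is tested across follow-up visits alone, a fall complete by month 3 leaves those visits equal and the rate at 5%. That test would equally miss a dog effect complete by month 3.

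**With pre-pairing data.** I took a mixed model with a common linear slope and a step at pairing, correlation 0.80, 1 to 8 pre-pairing visits and no between-Veteran slope variance. A 2-point linear drift over 24 months then gives a 5.0% rejection rate for the step. The SE of the step is 0.47 to 0.72 points at N = 200 for SD 10 to 15. Multiplying by √(200/187) = 1.034 gives about 0.49 to 0.74 at N = 187.

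**The case against.** The strongest reply has four parts.

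- **The size of any drift is unknown.** Veterans enter after at least three months of treatment, so early response may precede baseline. This stands. The drifts above show how much it would take to trigger the test, not what will happen. The criterion sets a minimum duration, however, and does not require symptoms or therapy to be stable.
- **The calculated test is not the one written.** This also stands and is disclosed above. The written test compares groups that no longer exist.
- **A change in care would be seen elsewhere.** Medication is examined under Hypothesis 1B and mental health utilization under Hypothesis 2A. That is a fair point about the study as a whole, but neither analysis is linked to the Hypothesis 1A conclusion.
- **Dogs are presented as an adjunct to treatment, and a pet-dog study offers a comparison.** The adjunct wording is background and does not limit the conclusion. The pet-dog comparison is exploratory, has no power analysis, and stops at six months.

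A reader might go further and infer that 1 to 2 points of drift is enough to make the test fire. The figures do not support that: a 1-point mean fall rejects in a minority of trials (19 to 37%) on the main contrast. A reader might also infer that adjusting for therapy and medication would isolate the dog's effect. The Significance section suggests animals may improve rapport and retention in therapy, medication use is itself a Hypothesis 1B outcome, and care may be stepped up when symptoms worsen. These variables may be mediators or responses, so adjustment cannot decide the question.

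**Conclusion.** The concern holds in a limited form. The documents establish that Hypothesis 1A can test only change over time in one group, that PTSD treatment is universal by rule, and that nothing in the analysis or its wording separates the dog from treatment, natural recovery or regression to the mean. That conclusion does not depend on any assumed number.

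The size does. On the assumed contrast, with SD 10 to 15 and N = 187, a background mean fall of about 2 to 3 points would usually be declared a benefit with no dog effect, and 1 point already raises the error to roughly four to seven times the nominal 5%. The documents do not show that such a fall will occur, so they do not support saying that a positive result would be false. They support saying that it could not be interpreted as the dog's effect.

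**What to change.** In the Analysis section, Hypothesis 1A:

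1. Replace the between-group wording with a one-group analysis. State that the pre-to-post PCL change reflects a dog added to required PTSD treatment, together with that treatment and time, and will not be reported as the effect of the dog alone.
2. Define baseline as the last assessment before pairing. Fit a mixed model to all pre- and post-pairing PCL scores, with a pre-pairing time slope and a change at pairing. The baseline score should enter as an outcome in this model, not as a covariate as well.
3. Optionally, report PCL change with therapy visits and type and medication added, as a descriptive sensitivity analysis only. Do not make persistence after that adjustment the condition for calling a change dog-related.

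The cost is some extra analysis on data already scheduled, with no new visits, and a more cautious conclusion. The second item relies on drift being linear and the same before and after pairing. A dog effect that builds gradually would be partly absorbed by the common slope, and allowing the slope to change at pairing needs Veterans with at least two pre-pairing assessments. These limits should be stated with the result.

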TASK	YEAR 1				YEAR 2				YEAR 3				YEAR 4				YEAR 5			
	Apr 2011	June 2011	Aug 2011	Oct 2011	Jan 2012	Apr 2012	Aug 2012	Oct 2012	Jan 2013	Apr 2013	Aug 2013	Oct 2013	Jan 2014	Apr 2014	Aug 2014	Oct 2014	Jan 2015	Apr 2015	Aug 2015	Oct 2015
Start up activities, finalize data collection forms, hire and train data collectors	Shaded																			
Renewal training for data collection				Shaded			Shaded													
Advertisement/promotion of study	Shaded	Shaded	Shaded	Shaded																
Recruit participants, collect baseline	Shaded	Shaded	Shaded	Shaded	Shaded															
STUDY HOLD**					Blue	Blue	Blue	Blue	Blue	Blue										
Collect 3-, 6-,9-, 12- 18- and 24-month data on enrolled veterans			Shaded	Shaded	Shaded	Shaded	Shaded	Shaded	Shaded	Shaded	Shaded	Shaded	Shaded	Shaded	Shaded	Shaded	Shaded	Shaded	Shaded	Shaded
Enter data in electronic database and conduct on-going verification			Shaded	Shaded	Shaded	Shaded	Shaded	Shaded	Shaded	Shaded	Shaded	Shaded	Shaded	Shaded	Shaded	Shaded	Shaded	Shaded	Shaded	Shaded
Conduct statistical analyses and summarize findings																				
Apply for additional funding to support follow up work																				
Dissemination of Findings																				
Prepare manuscripts																				Shaded

\*\* Because of ongoing vendor issues, enrollment was stopped for a second time and new vendors have been awarded contracts. Study will extend beyond the three year period utilizing Veterans who signed consent prior to second hold.

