*Screening Visit:* Once a Veteran has agreed to participate in the study, they will be asked to participate in a screening visit. Once the informed consent process is finalized, eligibility criteria will be confirmed. A review of CPRS records will be conducted by the study team to verify the Veteran truly meets all criteria. At this time, if all criteria are met, all baseline questionnaires will be completed and field notes taken. For safety reasons, Veterans who have children younger than 10 years of age in the home for more than 8 hours per day, one day per week or more will be excluded from the study. After 20 dogs have been placed without incident, this criterion will be revisited to potentially allow these Veterans to participate.

- The study team will perform a home evaluation visit prior to referring Veterans to a vendor. This visit will be to ensure the environment is safe and suitable for a

dog. A home environment checklist has been developed and will guide the study team in assessing the environment. An information sheet that provides details to Veterans regarding why and how the home visit will be conducted will be provided to Veterans when Informed Consent is obtained. During the visit, the team will check to see that there is an area for a dog to exercise, relieve itself, sleep, as well as making sure hazardous plants or chemicals are not within reach of a dog. All family members that will be living in the home will be expected to meet with the study team to ensure they understand the study requirements and are on board with bringing a dog into the home. If any issues are identified by the study team during the home evaluation the Veteran will have 3 weeks to fix the issues and reschedule a follow up home evaluation visit. If during the follow up home evaluation the study team determines that the issues are not fully resolved the Veteran will have one additional week to remedy the issues and reschedule a final home evaluation. If the issues remain unresolved the Veteran will be withdrawn from the study. Once the home evaluation has been approved the Veteran will be provided with contact information for the vendor. The Veteran will be instructed to contact the vendor and will be placed on the waiting list. The Veteran will be encouraged to review home owner/rental insurance policy to include a dog and be required to obtain a license for their service dog per local laws.

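### Enrolling up to 220 with 15% drop-out (n=33) gives at most 187 expected completers, not the 200 the plan states.

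*Combined protocol and SAP*

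**What the plan says.** All the figures stand together in the Sample text of the Design section (Research Design and Methods).

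- **Enrolment:** "We will be enrolling up to 220 Veterans to be paired with service dogs". The same paragraph repeats 220 as the upper limit on total recruitment.
- **Earlier experience:** "The previously cited longitudinal study had only an eight percent attrition rate". Because this population differs, "we will plan on a higher attrition rate".
- **Planned loss:** "we are estimating a 15 percent drop-out rate", with n=33 in brackets and a statement that over-recruitment will cover it.
- **Expected completers:** the recruitment numbers are said to rest on the expectation that "200 individuals* will complete the study".

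Other sections bear on how these figures should be read. Design says that the no-dog control group has been dropped, so all completers must come from the service dog group. The note under the Timeline table reports a second stop to enrolment and adds: "Study will extend beyond the three year period utilizing Veterans who signed consent prior to second hold".

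On losses before pairing, the text points two ways. Design treats vendor acceptance as part of eligibility: "Recruits who do not meet all criteria, including vendor criteria, will be ineligible to participate". Participant Recruitment and Informed Consent takes baseline data at consent and then allows withdrawal before any dog is placed. One ground is a failed home evaluation: "If the issues remain unresolved the Veteran will be withdrawn from the study". Another is having no dog after 48 months.

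**The concern.** The completer number is a stated design figure, given as the reason for the recruitment numbers, and the plan's own enrolment cap and drop-out rate do not produce it. The plan allows for more attrition than the earlier study had, but the allowance does not reach the completer figure. The 200 is close to what 220 would yield at the earlier study's 8%, the rate the plan says it will exceed.

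What is at stake is mainly the standard for judging retention. Design promises monthly monitoring of recruitment and retention. Measured against 15% loss, a fully enrolled trial with 187 completers is on plan; measured against 200, the same trial is 13 short. The plan gives both standards and no way to choose between them.

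The stated power is not at stake. The power statement in the Sample text gives no sample size, and the one headed Power analysis for Hypotheses 1 uses 65 per group.

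**Working it through.** **Inputs, all from the Sample text:** maximum enrolment N = 220; drop-out d = 15% (n = 33); expected completers 200; attrition in the earlier study 8%.

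**1. Reproduce the plan's figures.**
- Drop-outs = N × d = 220 × 0.15 = 33. This matches the stated n=33, so the 15% is taken from the 220 enrolled. (15% of 200 would be 30.)
- Completers = N × (1 − d) = 220 × 0.85 = 187. The stated 200 is not reproduced.
- Gap = 200 − 187 = 13, and 13/200 = 6.5%.

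**2. Work backwards from 200.**
- Enrolment needed at 15% loss = 200/0.85 = 235.3, so 236.
- Multiplying up instead of dividing, a common slip, gives 200 × 1.15 = 230, which is not 220 either.
- Loss implied by 220 enrolled and 200 completing = 20/220 = 9.1%.
- At 8%: 220 × 0.92 = 202.4. The pair 220 and 200 therefore fits a loss of about 8% to 9%.

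**3. Could chance close the gap?** Assume each of 220 participants independently has a 15% chance of dropping out. The exact binomial probability of 200 or more completers is then about 0.6%.

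**4. Effect on precision.** As an illustration, assume a simple paired comparison with two-sided 5% and 80% power (noncentral t). This is not the mixed model planned in the Analysis section. The detectable change, in SD of change, is 0.199 with 200 completers and 0.206 with 187.

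**5. If the 15% covers only loss after pairing.** The plan gives no rate for loss before pairing, so the rates below are assumptions chosen to show the range. Completers = 220 × (1 − assumed loss) × 0.85, rounded down to whole people.

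| Assumed loss before pairing | Calculation | Completers | Detectable change (SD of change) |
|---|---|---|---|
| 0% | 220 × 0.85 = 187 | 187 | 0.206 |
| 5% | 220 × 0.95 × 0.85 = 177.65 | 177 | 0.212 |
| 10% | 220 × 0.90 × 0.85 = 168.3 | 168 | 0.217 |
| 20% | 220 × 0.80 × 0.85 = 149.6 | 149 | 0.231 |

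**6. Why the meaning of completion matters.** Preliminary Studies reports 186 enrolled in the wheelchair assistance dog study. Of these, 14 were withdrawn or dropped out (14/186 = 7.5%), but only 123 completed all five collection points (123/186 = 66%). The same study can thus be described as losing about 8% or as having 66% complete data, depending on the definition.

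**The case against.** Nobody can dispute the subtraction; the objections concern remedy, scope and importance.

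*The text does not show which figure is wrong.* Enrolment could be 236, drop-out about 9%, or completers 187. The 15% might even be out of date, since the plan has abandoned its rule of dropping people who fail to return questionnaires. It is true that any of the three could be changed. But the documents do not say that the 15% predates that change, and a rate near 9% would undercut the stated intention to allow for clearly more loss than 8%. Raising enrolment to 236 means 16 more Veterans and dogs. Correcting the completer figure keeps both of the sponsor's own inputs.

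*The 15% of those enrolled naturally includes losses while waiting.* This is a reasonable reading. The recruitment section has the study team screen already enrolled Veterans against vendor criteria, and Human Subjects counts the repeated baseline assessments as participation. Against it, Design and the inclusion table make vendor acceptance a condition of entry. No sentence settles the matter, so a clarification is worth requesting, but the main finding does not depend on it. The scenarios in step 5 have no documentary rate behind them and are illustration only.

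*187 is not a strict ceiling.* This stands as a point of wording. It is the expected number at full enrolment and 15% loss; better retention could exceed it.

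*The consequence is small.* This also stands. The planned mixed models are chosen partly to handle missing data, data are to be managed by intent to treat, and no decision rule is tied to 200.

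Nothing elsewhere reconciles the figures. The over-recruitment remark is followed at once by the same limit of 220, and the contingency of adding VA hospitals serves only to reach the enrolment numbers.

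**Conclusion.** The concern holds. On the plan's own enrolment limit and drop-out rate, the expected number of completers is at most 187, so the stated 200 is too high by at least 13 (6.5%). This rests only on figures in one paragraph and on the 15% applying to the 220 enrolled, which the stated n=33 confirms. The shortfall is larger if fewer than 220 are enrolled, which the second enrolment stop makes plausible, or if losses before pairing come on top of the 15%.

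It is an inconsistency that should be corrected, with little effect on precision and none on the stated power.

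**What to change.** In the Sample text of the Design section:

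1. Replace the expectation of 200 completers with at most 187 (220 × 0.85), leaving the enrolment limit and the 15% as they are.
2. Define completion, for example as providing the final assessment or as providing all scheduled assessments.
3. State whether the 15% includes losses between consent and pairing (home evaluation, vendor acceptance, no dog by 48 months). If it does not, give that loss as a separate rate and lower 187 accordingly.

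The cost is one corrected number and one or two sentences, with no added participants, visits or data. The only drawback is a slightly less favourable completer figure. If the sponsor prefers to keep 200, it must either plan for 236 enrolled or justify a loss of no more than 9.1%.
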